### **Statistical analyses**

Based on previous randomized intervention studies of dietary fat quality and effects on lipoproteins, at least n=222 participants are required (for alpha = 0.05 and beta = 0.10) to detect an effect in LDL cholesterol of 0.175 mmol/L (~5%), which is an effect slightly exceeding that in most previous studies, parallels within-individual day-to-day variation (at double sampling), and has some clinical significance. This calculation takes into account a 20% loss to follow-up in the intervention group and a contamination effect of 5% in the control group.

The results will be analyzed according to intention-to-treat principle. Missing data at follow-up will be handled by imputing the baseline value. For LDL cholesterol, the mean value of the double analyses at days -3/0, 18/21 and 180/183 will be used. The CV of the biological variation will thus be decreased from 7 to 5%. Between-group comparisons for effects on all outcomes will be performed as a generalized linear model (GLM) in SPSS software, adjusted for factors *a priori* considered likely to modify effects (baseline values, BMI, age and sex). As sensitivity analyses, also unadjusted, non-parametric testing (Mann-Whitney U-test) will be performed. P<0.05 will be considered as statistically significant.

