P<0.05 will be considered as statistically significant for primary outcomes. For secondary outcomes, significance testing is not as essential as they are mainly hypothesis generating.

17. Adjustment for multiple analyses

The primary outcome is change in LDL cholesterol at 3 weeks and 6 months. The power calculations have been performed for between-group differences at 6 months and this analysis is considered the primary outcome of the study. Thus, no adjustment for multiple analyses will be performed.

18. Confidence intervals

N/A.

Adherence and protocol deviations

19a. Definition of adherence to the intervention

Being randomized and completing the trial (day 183) is considered as sufficient for adherence. For the visit at 3 weeks, no more than 2 days' deviation from protocol will be allowed. For the visit at 183 days, no more than 2 weeks' deviation will be allowed.

19b. Description how adherence will be presented

No specific information on adherence will be presented, besides no. of participants randomized and completing the trial at 3 weeks and 6 months, and no. excluded before and after randomization, with reasons.

19c. Definition of protocol deviations

Deviations from time schedule. Failing to be overnight fasting at time points 2, 4 or 6.

19d. Description of which deviations will be summarized

In cases in which blood samples are taken on the wrong day, the no. of deviations and number of days' deviation from protocol will be reported for each time point. Also, the number indivduals who failed to be completely fasting at time points 2, 4 and 6 will be given.

20. Analysis populations

Study populations will be analyzed according to intention-to-treat principles.

Section 5. Trial Population

21. Screening data

N/A (not collected).

22. Eligibility criteria

Inclusion criteria: patients listed at the health care centre, wish to improve blood lipoproteins, ages 18-99 years.

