Secondary outcomes: Change in HDL cholesterol, total cholesterol, fasting triglycerides, apo B, apo AI, apo B:AI, fasting glucose, HbA1c, systolic and diastolic blood pressure, weight, BMI and waist circumference at 6 months and 3 weeks. No. and proportion of individuals that achieve a $\leq 0\%$, > 0 to < 10% or $\geq 10\%$ reduction in LDL cholesterol from baseline, after 6 months and 3 weeks. Change in LDL cholesterol at 6 months and 3 weeks, in responders at 3 weeks (≥10% reduction in LDL cholesterol from baseline). No. and proportion of individuals misclassified at 6 months and 3 weeks with only sample 2, 4 and 6 included in analyses. Estimated cost of intervention. Associations of food choices (total no. and no. and proportion of total X:s for each dietary advice in food record table) with change in LDL cholesterol, and with HDL cholesterol, total cholesterol, fasting triglycerides, apo B, apo AI, apo B:AI, fasting glucose, HbA1c, systolic and diastolic blood pressure, weight, BMI and waist circumference at 6 months and 3 weeks. Reasons stated for wanting to improve blood lipoproteins, and associations with total no. and percentage of total of X:s in food record table and with changes in LDL cholesterol, HDL cholesterol, total cholesterol, fasting triglycerides, apo B, apo AI, apo B:AI, fasting glucose, HbA1c, systolic and diastolic blood pressure, weight, BMI and waist circumference at 6 months and 3 weeks. No. of individuals that develop impaired fasting

glucose, and elevated ALT at 6 months and 3 weeks. Change and average variation (CV) in LDL Cholesterol at 21 vs. 18 days and at 183 vs. 180 days.

Possible future analyses: Change in plasma Lipoprotein(a), serum PSCK9 and genes involved in lipid metabolism at 6 months and 3 weeks.

26b. Specific measurements and units

LDL cholesterol (direct method), HDL cholesterol, total cholesterol, fasting triglycerides and glucose in mmol/L.

Apo B and apo AI in g/L.

HbA1c in mmol/mol.

ALT in µkat/L.

TSH in mU/L.

Weight (in light clothing) in kg.

Height and waist circumference in cm.

BMI as kg/m^2 .

Systolic and diastolic blood pressure in mm hg.

Age at randomization in X.X years

Type 2 diabetes is defined according to current diagnostic criteria.

Impaired fasting glucose is defined as fasting P-glucose 6.1 - 6.9 mmol/L.

26c. Specific calculations

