For LDL Cholesterol baseline (BL) values will be calculated as the arithmetic mean of values at day -3 and day 0 [(d-3+d0)/2], similarly, values at 3 weeks will be calculated as the arithmetic mean of values at days 18 and 21 [(d18+d21)/2] and values at 6 months will be calculated as the arithmetic mean of values at days 180 and 183 [(d180+d183)/2].

For all continuous variables, absolute change from baseline (Δ) will be calculated at 3 weeks and 6 months as [Δ = 3w - BL and 6m - BL]. Relative change from baseline (% Δ) will be calculated as [% Δ = (3w - BL)/BL and (6m - BL)/BL].

As a sensitivity analysis, variables in the GLM with non-normal distribution will be log transformed (otherwise, no transformations will be performed).

Analysis methods

27a. Analysis methods and presentation of results

Between-group differences for change from baseline (Δ) in continuous variables will be significance tested using a general linear model (GLM). For LDL cholesterol, the results will be presented as a figure with boxplots displaying values at BL, 3 weeks and 6 months for each group. Also, a boxplot of Δ -values at 6 months will be presented for each group. The results will be given in a table format, displayed as mean±SD change from baseline, and P-values for difference between groups.

Difference in mean change from baseline in LDL cholesterol (and triglycerides for control group) between 21 and 18 days and 183 vs. 180 days will be analyzed with t-tests.

Secondary outcome no. 4 (success rate) i.e. the no. and proportion of individuals that achieve a $\leq 0\%$, >0 to <10% or $\geq 10\%$ reduction in LDL cholesterol from baseline will be analyzed by logistic regression, adjusted for age, sex and baseline BMI. No. of individuals that develop impaired fasting glucose will be compared between groups with Fisher's exact test (unadjusted).

Secondary outcome no. 8 (effective food choices) will be analyzed and presented as linear regressions between number of X:s for food choices 1-13 (and the total number of X:s) and change in LDL cholesterol (or Triglycerides within Control group) at 3 weeks and 6 months.

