Further, subgroup analyses will be performed in young (<65 years) vs elderly (65+) individuals, in order to establish whether results are homogenous in these subgroups, for guidance of future studies.

28. Missing data

When data are missing due to loss to follow-up, baseline values will be imputed. If only one time point 3 or 5 is missing (LDL cholesterol at d18 or d180), the mean LDL

cholesterol value will instead be assumed to be the exact value at time point 4 or 6 (d21 or d183).

29. Additional analyses

For possible future analyses (see 26a. secondary outcomes), analyses will be performed with similar methods as other continuous/categorical variables.

30. Harms

Reported adverse effects (if any) will be described in text or table format, depending on the outcome. No serious adverse effects are expected and severity will not be summarized separately.

31. Statistical software

IBM SPSS Statistics 25 will be used for all analyses.

32. References

Data management plan, standard operating procedures, dietary advice, food records and study letters will be stored separately and not provided at trial registry during the study. No statistical master file has yet been created and public access will not be granted.

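### Participants lost to follow-up enter the Fisher test for new impaired fasting glucose as non-events, although they were not measured at that time point

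*SAP*

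**What the plan says.** SAP 26a lists among the secondary outcomes the number of participants who newly have impaired fasting glucose or raised ALT at each follow-up: "glucose, and elevated ALT at 6 months and 3 weeks". SAP 26b supplies the glucose definition: "Impaired fasting glucose is defined as fasting P-glucose 6.1 - 6.9 mmol/L". No threshold is given for ALT. SAP 27a names the test for glucose only: "No. of individuals that develop impaired fasting glucose will be compared between groups with" Fisher's exact test, unadjusted.

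Three general rules then apply:

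- SAP 28: "When data are missing due to loss to follow-up, baseline values will be imputed". The one special rule in that item is for a missed first LDL sample of a pair.
- Protocol, Statistical analyses: "Missing data at follow-up will be handled by imputing the baseline value".
- SAP 20: "Study populations will be analyzed according to intention-to-treat principles".

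Nothing exempts binary outcomes. The sensitivity analyses in SAP 27e cover means of continuous outcomes only. SAP 30 (Harms) has no rule for laboratory values. On expected loss, the protocol says of its sample size: "This calculation takes into account a 20% loss to follow-up in the intervention group". It gives no loss figure for control.

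**The concern.** To develop a condition is to be free of it at baseline and to have it later. If the later value is set equal to the baseline value, the participant cannot become a case, whatever happened. Under intention to treat that person still sits in the Fisher table as a non-event. Someone who develops impaired fasting glucose at 3 weeks and is then lost is returned to the baseline state at 6 months.

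For the LDL outcome, carrying baseline forward can be defended as cautious, because it assumes no benefit in those lost. For an unfavourable event it works the other way, because it assumes that nobody lost had the event. The stakes are a rate that is too low in any arm with loss, and a distorted comparison when loss differs between arms.

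**Working it through.** **The plan's own figure.** There is none to reproduce. The documents give no expected rate, sample size or power for impaired fasting glucose or ALT. The sample-size calculations concern LDL cholesterol only.

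**Inputs from the documents**
- 113 participants randomised 1:1 (SAP 9 and 11), taken as 57 and 56.
- 20% loss in the intervention group (Protocol, Statistical analyses; SAP 11). This is a planning figure.
- Fisher's exact test (SAP 27a), P<0.05 (SAP 16; Protocol).

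**Assumptions, shown as ranges**
- Control loss of 0%, 10% or 20%.
- True event rates of 5% to 30%.
- Everyone is free of the condition at baseline. This slightly overstates the number at risk.

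**Step 1: rate in one arm.** Let p be the rate in completers and d the fraction lost. Imputed participants add no cases but stay in the denominator, so

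analysed rate = p × (1 - d).

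With p = 10% and d = 20%: 0.10 × 0.80 = 8%. The number of cases is the same with or without imputation. Only the non-event cell and the denominator differ.

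**Step 2: dependence on those lost.** If lost participants would have had m times the completers' rate, the true rate is p(1 - d) + m·p·d. For p = 10% and d = 20%:

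| m | True rate | Analysed rate | Relative fall |
|---|---|---|---|
| 0 | 8% | 8% | 0% |
| 0.5 | 9% | 8% | 11% |
| 1 | 10% | 8% | 20% |
| 2 | 12% | 8% | 33% |

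So the factor (1 - d) is exact only at m = 1. Imputation is right only at m = 0.

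**Step 3: comparison of arms.** With equal true rates and m = 1, the analysed risk ratio is (1 - d₁)/(1 - d₀), where d₁ is intervention loss and d₀ control loss:

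- 20% v 0%: 0.80/1.00 = 0.80
- 20% v 10%: 0.80/0.90 = 0.89
- 20% v 20%: 0.80/0.80 = 1.00

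**Step 4: Fisher's test.** Full enumeration of the 2×2 tables, two-sided P<0.05, loss 20% v 0%. Imputed: 57 v 56, with the intervention rate multiplied by 0.80. Completers: 57 × 0.80 ≈ 46 v 56.

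| True rates, intervention v control | Imputed | Completers | No loss |
|---|---|---|---|
| 30% v 10% (power) | 43% | 69% | 72% |
| 20% v 10% (power) | 10% | 25% | 24% |
| 20% v 20% (type I error) | 7.1% | 3.8% | – |

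With loss of 20% v 10% and equal true rates of 5% to 20%, the type I error with imputation is 1.6% to 4.6%, which stays below 5%.

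**The case against.** The strongest case on the other side is that little depends on this.

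- **A count is planned, not a rate.** SAP 26a asks for number and proportion for the LDL categories, but only for number here, and imputation leaves that number unchanged. This stands. What remains is the Fisher table, which needs non-event cells, and any rate that is reported on all randomised.
- **ALT has no test.** This also stands. A reader might infer that the rule lowers the results for both conditions alike. The documents support that for ALT only if its count is turned into a proportion of all randomised.
- **Unequal loss is an assumption.** A reader might infer from the 20% figure that the comparison is bound to favour the intervention. The documents give no control loss and no actual loss by arm, and equal loss leaves the risk ratio at 1.00. The ratio of 0.80 is the extreme case.
- **These are not labelled as harms.** The SAP lists them as secondary outcomes, apart from item 30, and item 16 calls secondary outcomes mainly hypothesis generating. This bears on severity and does not alter the mechanism.
- **A reader could undo it.** SAP 23 to 25 promise loss by group and baseline impaired fasting glucose, so the completers' comparison could be approximated. That is partly true, but the published P value would still come from the imputed table.
- **The remedy has its own assumption.** Analysing those measured is unbiased only if loss is unrelated to glucose. That is fair. It is still weaker than assuming that no lost participant had the event.

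It may also be said that an analyst would use observed cases anyway. The written rules say otherwise, and no passage overrides them.

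**Conclusion.** The point holds for the Fisher test on impaired fasting glucose. As written, SAP 20 and 28 score unmeasured participants who were free of the condition at baseline as non-events. Any rate on all randomised is then the completers' rate times (1 - loss), which is 20% too low in relative terms at 20% loss if those lost resemble completers.

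The effect on the comparison depends on control loss. A true risk ratio of 1.00 becomes anything from 0.80 to 1.00 over an assumed control loss of 0% to 20%. The fall in power from 69% to 43% rests on 20% v 0% loss and on assumed rates of 30% v 10%.

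Severity is minor. The case counts are right, the outcomes are secondary and hypothesis generating, and no efficacy conclusion depends on the test. The documents do not support reading this as an understatement of harm in general, or as a proven bias towards the intervention.

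**What to change.** Add to SAP 28, in substance: baseline imputation does not apply to new impaired fasting glucose or new elevated ALT. At each time point, report by arm the number of cases together with the number of participants who were measured at that time point and were free of the condition at baseline. Use those denominators in the Fisher test for impaired fasting glucose. The intention-to-treat version with imputation may be kept as a sensitivity analysis.

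This needs no new data. The cost is slightly smaller denominators (about 46 instead of 57 in the intervention group at 20% loss) and the assumption, to be stated in the report, that loss is unrelated to glucose or ALT.

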- What are the reasons given for wanting to reduce LDL cholesterol? Is there any association between reasons given and effect on LDL cholesterol?

Section 3. Study Methods

9. Trial design

The study design is a pragmatic randomized controlled dietary trial, with two parallel arms. The allocation ratio is 1:1. Both groups will receive dietary advice in sealed numbered envelopes. The intervention group will receive advice for reducing LDL cholesterol, whereas the control group will receive similar advice, but instead proven effective for reducing fasting triglycerides. The participants will not be aware of which group is considered as active intervention. Participants were recruited and randomized May to October 2018 and data collection is finished April 18th 2019.

10. Randomization

The allocation sequence is created by an external agent and performed in blocks (size unknown to investigators). The allocation sequence will be concealed until data collection has been completed.

11. Sample size

A primary power calculation was performed based on previous randomized intervention studies of dietary fat quality and effects on lipoproteins. At least n=222 participants were required (for alpha = 0.05 and beta = 0.10) to detect an effect in LDL cholesterol of 0.175 mmol/L (~5%), which would slightly exceed that in most previous studies, parallel within-individual day-to-day variation (at double sampling), and have some clinical significance. This calculation took into account a 20% loss to follow-up in the intervention group and a contamination effect of 5% in the control group.

In September 2018, during the end of recruitment process, another power calculation was performed in order to examine the power given the current recruitment status (n=104). For alpha = 0.05 and beta = 0.20, the minimum number of participants required was n=106 (n=94 without 5% contamination). Thus, the recruitment was considered as finished at Oct 16th, when n=113 participants were included (as the number of volunteer participants had faded, and power was considered sufficient, if not optimal).

12. Framework

The study is a dietary intervention with clinical and experimental outcomes.

13. Stopping interim analyses

N/A.

14. Timing of final analysis

All analyses will be performed once data collection is finished, April 18th 2019.

15. Timing of outcomes assessment

N/A.

Section 4. Statistical principles

Confidence intervals and P values

16. Level of statistical significance

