Secondary outcome no. 9 (stated reasons) will be categorized into main groups of reasons according to given responses (one, two or three compared to none stated), no. in each group and mean changes in LDL cholesterol (or triglycerides) as well as total number of X:s (and proportions of total number of possible X:s for both groups combined) will be given as means+SD in table format. For within-group effects on mean LDL cholesterol at 3 weeks and 6 months, paired t-tests will be performed in intervention group (the same for triglycerides in control group). For proportion of total X:s, differences compared with reference group (none stated) will be analyzed by Mann Whitney U-test.

27b. Adjustment for covariates

Comparisons of means in the GLM will be adjusted for the baseline value of the variable, baseline BMI, age and sex.

For success rate, the logistic regression will be adjusted for the covariates baseline LDL cholesterol, baseline BMI, age and sex.

Linear regressions for food choices and lipoproteins will be unadjusted.

27c. Tests for assumptions

Normality of data will be determined by visual inspection of histograms and QQ-plots. No other tests for assumptions will performed. The underlying assumptions of the GLM will be tested by examining residuals.

27d. Alternative methods if distributional assumptions do not hold

As a sensitivity analysis, variables in the GLM with non-normal distribution will be log transformed (otherwise, no transformations will be performed).

27e. Planned sensitivity analyses

For all comparisons of means of continuous outcomes, unadjusted Mann Whitney U-tests will be performed as sensitivity analyses.

27f. Planned subgroup analyses

In order to investigate whether different baseline characteristics are associated with success rate (outcome no. 4), responders (≥10% decrease in LDL cholesterol or Triglycerides) and non-responders at 3 weeks will be analyzed with descriptive statistics regarding age, sex, baseline cholesterol, no. with diabetes and impaired fasting glucose, systolic and diastolic blood pressure, no. of X:s (total and for each food choice), and reasons stated (according to categories), separately for both study arms. Comparisons between responders and non-responders will be analyzed by t-tests and Fisher's exact test. Similar analyses will be performed for successful individuals at 6 months (≥10% decrease in LDL cholesterol or Triglycerides).

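### SAP 27a plans no comparison of continuous LDL change between stated-reason categories, although SAP 8 and 26a promise that association; only the dichotomised responder comparison in 27f links reasons to LDL

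*SAP*

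**What the plan says.** The aim in SAP 8 (Objectives) is direct: "Is there any association between reasons given and effect on LDL cholesterol". SAP 26a turns it into a secondary outcome. It lists "Reasons stated for wanting to improve blood lipoproteins, and associations with total no. and percentage of total of X:s in food record table", and continues with associations with change in LDL cholesterol and the other risk factors at 6 months and 3 weeks.

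The method is in the 27a paragraph on secondary outcome no. 9:

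- Reasons are "categorized into main groups of reasons according to given responses (one, two or three compared to none stated").
- Mean change in LDL (or triglycerides) and the diary marks, by category, "will be given as means+SD in table format".
- For mean LDL at 3 weeks and 6 months, "paired t-tests will be performed in intervention group (the same for triglycerides in control group").
- A comparison between categories is named for the diary marks only: "For proportion of total X:s, differences compared with reference group (none stated) will be analyzed by Mann Whitney U-test".

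SAP 27f adds a responder analysis: "responders (≥10% decrease in LDL cholesterol or Triglycerides) and non-responders at 3 weeks will be analyzed with descriptive statistics". Reason categories are among the characteristics compared. The analysis is separate in each arm, uses t-tests and Fisher's exact test, and is repeated at 6 months.

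**The concern.** The aim is about a difference between categories: do people with one kind of reason change their LDL more than people with another? The LDL test named for this outcome has no category contrast in it. A reader of the eventual table would have a mean and SD per category, perhaps a before-after P-value, and no estimate of how much the categories differ or how uncertain that difference is.

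If before-after P-values were shown per category, the natural misreading would be to treat a significant category beside a non-significant one as evidence of an association. A before-after change also has no control, so it can include drift that has nothing to do with the advice.

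At stake is one stated aim. The primary comparison of the arms is not affected.

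**Working it through.** **Step 1. Match the promise to the method.** No figure in the documents depends on this point, so the first check is of the text.

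| Place | Contrast between reason categories? | Variable |
|---|---|---|
| SAP 8 and 26a | Promised | Change in LDL, among others |
| 27a, no. 9, table | No test or interval | Change in LDL or triglycerides, diary marks |
| 27a, no. 9, paired t-test | No | LDL against own baseline, intervention arm |
| 27a, no. 9, Mann-Whitney | Yes, against none stated | Proportion of diary marks only |
| 27a, opening GLM | No, compares trial arms | All continuous outcomes |
| 27e, Mann-Whitney sensitivity | No; repeats planned comparisons of means, and none by reason is planned | Continuous outcomes |
| 27f | Yes, responders against non-responders, per arm | LDL or triglycerides cut at a 10% decrease |

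The neighbouring outcome no. 8 (food choices) does get a regression on LDL change in 27a. The SAP therefore did not leave all its exploratory associations untested.

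**Step 2. Read the paired t-test both ways.** The sentence does not say whether the test is run once or per category. Run once on the intervention arm, it ignores reasons. Run per category, it gives separate before-after results that are never set against each other. Neither reading estimates the association.

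**Step 3. Illustrate the per-category reading.** This step applies only if the tests are run per category, which the SAP does not confirm.

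Inputs from the SAP: 113 randomised 1:1, so about 56 in the intervention arm; a change of 0.175 mmol/L (borrowed from the design effect in SAP 11); alpha 0.05 (stated in SAP 16 for primary outcomes, borrowed here).

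Assumptions: SD of change 0.35 or 0.50 mmol/L (no SD is given); two groups that do not overlap; the same true change in both, so no association exists.

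The power of each paired t-test, p, comes from the noncentral t distribution with n − 1 degrees of freedom and noncentrality 0.175/(SD/√n). The chance that exactly one group is significant is p₁(1 − p₂) + p₂(1 − p₁).

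| SD | Split | p₁ | p₂ | Exactly one significant |
|---|---|---|---|---|
| 0.35 | 28/28 | 0.723 | 0.723 | 0.40 |
| 0.35 | 20/36 | 0.565 | 0.831 | 0.46 |
| 0.35 | 10/46 | 0.293 | 0.913 | 0.67 |
| 0.50 | 28/28 | 0.431 | 0.431 | 0.49 |
| 0.50 | 20/36 | 0.318 | 0.533 | 0.51 |
| 0.50 | 10/46 | 0.168 | 0.642 | 0.59 |

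Worked example, SD 0.35, split 10/46: 0.293 × 0.087 + 0.913 × 0.707 = 0.025 + 0.645 = 0.67.

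A simulation of 20,000 trials per row agreed. In it, a direct two-sample comparison of change between the groups was falsely significant in 4.9% to 5.2% of trials.

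The result depends on the assumed SD. With two equal groups and SD 0.25, each test has power 0.946 and the disagreement falls to 2 × 0.946 × 0.054 = 0.10.

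**The case against.** **The SAP does test reasons against LDL.** A reader who stops at 27a might infer that the SAP contains no test of this association and cannot address its own aim. The documents do not support that. SAP 27f compares reason categories between LDL responders and non-responders, in each arm and at both times. This objection stands, and it limits the point to continuous change. Still, 27f is set up for the success-rate outcome (no. 4). It discards the size of the change, does not adjust for baseline LDL, and gives no LDL difference by reason. It also does not say which marker defines response in which arm.

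**Description may be enough.** SAP 16 calls secondary outcomes mainly hypothesis generating and gives significance testing less weight there. This stands as a reason for low severity. It does not explain a between-category test for the diary marks and none for LDL.

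**The illustration may never arise.** The wording speaks of the intervention group, so a single test on the whole arm is the plainer reading, and then no category P-values exist to misread. This stands. A reader might also infer that misleading patterns would appear in a large majority of trials. That would need a per-category reading, a chosen SD and several equal, separate categories. The SAP fixes none of these, and the sheet described in the Protocol (Methods) asks for three main reasons, so categories may overlap.

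**Regression to the mean.** A reader might infer a strong artefact in the before-after change. Eligibility has no LDL threshold and baseline is the mean of two samples, so the documents give little basis for a large one.

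**Conclusion.** The point holds in limited form. SAP 27a specifies no test or interval estimate of continuous LDL change between reason categories, although SAP 8 and 26a promise that association. The paired t-test named there answers a different question. The only planned link between reasons and LDL is the dichotomised, unadjusted, arm-by-arm comparison in 27f.

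This conclusion rests on the text alone. The 40% to 67% range is an illustration of why per-category before-after tests would be a poor substitute. It depends on the assumed SDs, the assumed splits into two separate groups and the per-category reading.

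Severity is low: the outcome is secondary and exploratory, and the primary result does not depend on it.

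**What to change.** For outcome no. 9 in SAP 27a:

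- Replace the paired t-tests as the inferential analysis with a linear model of LDL change in the intervention arm (triglyceride change in the control arm) on reason category, adjusted for the baseline value. Report category differences with 95% CIs and one overall test.
- State whether categories are kinds of reason or the number of reasons given. If a participant can fall into several kinds, use one yes/no indicator per kind, tested jointly.
- Fix the reference category before outcomes are looked at.
- Say what effect means. The within-arm model describes association with change and supplies no control. If the effect against control is meant, fit LDL change in both arms with a reason-by-arm term. The reasons question is on the sheet inside the allocation envelope, so this also assumes that allocation does not influence the answers.
- Keep within-arm change as description, and label the analysis exploratory.
- In 27f, state which marker defines response in each arm.

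The cost is SAP wording and one extra model on data already collected. The downside is low precision. With 56 in the arm and two groups, the 95% CI half-width for the difference is about 2.005 × SD × √(1/n₁ + 1/n₂), ignoring any gain from baseline adjustment. That is 0.19 mmol/L at SD 0.35 with 28/28, and 0.35 mmol/L at SD 0.50 with 10/46. Both exceed the 0.175 mmol/L design effect, so the intervals should be read as exploratory.
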